7.13.2. Vital Signs

Vital sign measurements will include temperature, systolic and diastolic blood pressure, pulse, respiratory rate, and oxygenation status (as measured by pulse oximetry or arterial blood gas).

Vital sign measurements will be obtained at the Screening Visit, the Randomization Visit (Day 1 pre-dose), on Day 1 following administration of study drug, daily during the Monitoring Period (if subject is hospitalized), on Day 22, on the day of hospital discharge (for subjects who are discharged between Day 40 and Day 90), at the Day 90 Safety Visit (if the visit occurs onsite), or Early Termination (if applicable). Oxygenation status will be determined at the Screening and Randomization Visits via measurement of arterial blood gas, provided the subject has an arterial line placed. If no arterial line is present, pulse oximetry may be used.

Descriptive statistics will be used to summarize vital signs measurements and change from baseline by each scheduled time point.

All vital sign assessments will be listed by subject.

7.13.3. Electrocardiograms

A 12-lead ECG will be performed for all eligible subjects at the Randomization Visit (Day 1 pre-dose), on Day 22, on the day of hospital discharge (for subjects who are discharged between Day 40 and Day 90), at the Day 90 Safety Visit (if the visit occurs onsite), or Early Termination (if applicable).

Quantitative ECG parameters (HR, PR, QRS, QT, and RR) will be summarized with descriptive statistics for baseline, post-baseline, and change from baseline by each scheduled time point.

The number and percent of subjects with normal, abnormal not clinically significant, and abnormal clinically significant ECG assessments will be tabulated.

All 12-lead ECG data will be listed by subject.

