NOTE: The results of the qualifying ETA culture must allow randomization to occur within 48 hours (or up to 60 hours with Medical Monitor approval) from the time the ETA sample was collected. Subjects with ETA culture results obtained after 60 hours showing heavy colonization of *S. aureus* may not be randomized and will be discontinued from the study.

3. Subject remains mechanically ventilated and, in the Investigator's opinion, will require ongoing ventilator support for at least 48 hours; and
4. Subject has, in the opinion of the Investigator, a probability of survival beyond 72 hours post-randomization.

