### **9.9 Electrocardiograms**

A 12-lead ECG will be performed for all eligible subjects at the Randomization Visit (Day 1 pre-dose), on Day 22, on the day of hospital discharge (for subjects who are discharged between Day 40 and Day 90), at the Day 90 Safety Visit (if the visit occurs onsite), or Early Termination (if applicable).

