5.2.7. Safety Endpoints

Safety endpoints are as follows:

1. Treatment-emergent adverse events (TEAEs)
2. Vital signs
3. Electrocardiograms (ECGs)
4. Laboratory parameters
5. Physical examinations

6. Radiographs and Imaging
7. Immunogenicity and anti-drug antibodies

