7.4. Baseline Definition

For all efficacy and safety endpoints, baseline is defined as the last measurement or assessment prior to the first and only dose of study drug.

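### The SAP summarises QT only without heart-rate correction, so change from a ventilated baseline can largely reflect heart rate; adding QTcF from the QT and RR already listed is a minor, inexpensive improvement

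*SAP*

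**What the plan says.** ECG is one of seven safety endpoints in SAP 5.2.7, and safety is part of the primary objective (protocol 2.1, SAP 4.1.1). SAP 7.13.3 plans three ECG outputs:

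- Interval summaries: "Quantitative ECG parameters (HR, PR, QRS, QT, and RR) will be summarized with descriptive statistics for baseline, post-baseline, and change from baseline", at each scheduled time point.
- An overall reading: "The number and percent of subjects with normal, abnormal not clinically significant, and abnormal clinically significant ECG assessments will be tabulated".
- Listings: "All 12-lead ECG data will be listed by subject".

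No corrected QT, correction formula or QT threshold appears in either document. Protocol 9.9 gives a schedule only: "A 12-lead ECG will be performed for all eligible subjects at the Randomization Visit (Day 1 pre-dose), on Day 22", then hospital discharge if that falls between Day 40 and Day 90, the Day 90 visit if onsite, or Early Termination.

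Under SAP 7.4, "baseline is defined as the last measurement or assessment prior to the first and only dose of study drug". Protocol 4.3 fixes the subject's condition shortly before that measurement: "Subject remains mechanically ventilated and, in the Investigator's opinion, will require ongoing ventilator support for at least 48 hours". Summaries are shown by treatment group (SAP 7.1).

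**The concern.** Raw QT shortens as heart rate rises and lengthens as it falls. The planned change score compares an ECG from a ventilated subject with one taken about three weeks later, or at withdrawal. Heart rate can plausibly differ between those two occasions, so a change in raw QT may say little about repolarisation. It can show lengthening where there is none, or conceal lengthening if heart rate has risen since baseline.

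Three things are at stake. Mean change within an arm is hard to read. No table counts subjects with a large corrected value or a large corrected increase. Heart-rate variation also adds noise to the comparison of arms. HR and RR are summarised alongside QT, but subject-level QTc cannot be recovered from arm means of QT and RR.

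The SAP is more exacting with laboratory data: section 7.13.4 pre-states liver thresholds and worst-value shift tables. The ECG section states no threshold.

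**Working it through.** **Inputs.** From the documents: the parameter list and ECG schedule (SAP 7.13.3, protocol 9.9), the baseline rule (SAP 7.4), and the planned event rates of 25% and 12.5% (SAP 6). The documents give no heart rates, QTc values or their variability, so those below are assumptions, shown over a range.

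**The plan's own figure.** The ECG section states no number. The only planned quantity used here is the effect size, and the sample size built on it reproduces. With pooled variance, two-sided 0.05, 80% power and no continuity correction,
n = [1.96·√(2·0.1875·0.8125) + 0.8416·√(0.25·0.75 + 0.125·0.875)]² / 0.125² = 152 per arm, as stated. The ECG point does not depend on n.

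**Formula.** Fridericia: QTcF = QT / RR^(1/3), so QT = QTcF × RR^(1/3), with RR = 60/HR in seconds.

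**1. Apparent change with no change in repolarisation.** QTcF held at 420 ms:

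- 100 bpm: 420 × 0.60^(1/3) = 354 ms
- 75 bpm: 420 × 0.80^(1/3) = 390 ms
- Difference: 36 ms

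Over QTc of 400 to 440 ms and heart-rate falls of 10 to 30 bpm (100 to 90, 90 to 80, 100 to 80, 110 to 80), raw QT rises by 12 to 40 ms under Fridericia and 17 to 56 ms under Bazett.

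**2. A true rise concealed.** QTcF goes from 420 to 440 ms. Raw QT change = 440 × (60/HR₁)^(1/3) − 420 × (60/HR₀)^(1/3):

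| HR at baseline → later | Raw QT change |
|---|---|
| 80 → 90 | +3 ms |
| 90 → 100 | +4 ms |
| 90 → 105 | −2 ms |
| 80 → 100 | −11 ms |

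Exact cancellation needs HR₁/HR₀ = (440/420)³ = 1.15, for example 80 to 92 bpm or 100 to 115 bpm.

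If heart rate does not change, there is little masking. At a steady 100 bpm, the 20 ms rise shows as 20 × 0.60^(1/3) = 17 ms.

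**3. Share of the variance of QT change due to heart rate.** Near 90 bpm the slope is (420/3) × 60^(1/3) × 90^(−4/3) = 1.36 ms per bpm. Taking heart-rate and QTc changes as independent,
share = (1.36·SD_HR)² / [(1.36·SD_HR)² + SD_QTc² × (60/90)^(2/3)].

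- SD_HR 5 bpm, SD_QTc 30 ms: 6%
- SD_HR 15 bpm, SD_QTc 20 ms: 58%
- SD_HR 20 bpm, SD_QTc 10 ms: 91%

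**4. Between-arm distortion through prevented pneumonia.** On the planned effect, 25% − 12.5% = 12.5% of subjects have a different pneumonia outcome by arm. If every such subject would otherwise be at 100 rather than 75 bpm at the later ECG, the spurious difference in arm means is 0.125 × 36 = 4.5 ms.

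**The case against.** The case for leaving the plan alone has substance.

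- **Placebo control.** A heart-rate shift shared by both arms largely cancels. A misleading comparison needs heart rate, or dropout, to differ by arm. This stands: a reader might carry the 36 ms over to the comparison of arms, but that figure is a within-subject shift. The corresponding bound through prevented pneumonia is about 4.5 ms. Even that requires every prevented case to be alive, to have an ECG and still to be tachycardic, although some pneumonias would have resolved by Day 22.
- **No evidence that heart rate dominates.** A reader might infer that raw QT change mostly tracks heart rate, or cannot be interpreted at all. The documents hold no heart-rate data, and the variance share runs from 6% to 91%, so only ‘can be dominated’ is supportable.
- **Masking in persistent tachycardia.** A reader might expect a true rise to be hidden in subjects who stay tachycardic. Step 2 shows that it is not. Masking needs heart rate to rise after baseline, which is the reverse of the usual picture of recovery.
- **Other safeguards.** Protocol 9.1 has clinically significant ECG abnormalities reported as adverse events, and SAP 7.13.1 tabulates treatment-emergent events by arm. With the three-category table and the listings, ECG safety is not confined to raw QT. None of these outputs, however, gives the distribution of QTc change or counts of outlying subjects.
- **Low prior concern.** Protocol 1.3 describes antibodies to bacterial toxins with no cross-reactivity in 33 human tissue types. Neither document identifies a repolarisation risk. This stands and limits the weight of the point.
- **It can be derived later.** True, since QTcF is a fixed function of listed data. But cut-offs chosen after unblinding carry less weight than those fixed beforehand.

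**Conclusion.** The concern holds as a minor point about a descriptive safety table. The only repolarisation interval summarised is uncorrected QT, and the planned change score spans a period over which heart rate can move. Under assumed heart rates, within-subject raw QT can shift by 12 to 40 ms (Fridericia) with no change in QTc, and a rise of about 10 to 20 bpm can offset a true 20 ms QTcF increase. The distortion of arm means through prevented pneumonia is at most about 4.5 ms, given the planned effect and a 100 versus 75 bpm contrast. The main losses are uninformative within-arm change, absent outlier counts and extra noise.

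The documents do not support saying that the QT results will be uninterpretable or that the comparison with placebo is seriously biased. The primary efficacy analysis and sample size are unaffected.

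**What to change.** In SAP 7.13.3:

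1. Add QTcF = QT / (RR in seconds)^(1/3), derived for each ECG from the QT and RR already listed.
2. Summarise QTcF and its change from baseline by arm and scheduled time point, beside the existing HR and RR summaries.
3. Tabulate by arm the number and percentage of subjects above cut-offs for the QTcF value and for its increase. The documents supply no cut-offs, so the sponsor should choose them and write them into the SAP before unblinding. SAP section 3 allows modification up to that point.
4. Keep raw QT in the listings.

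The cost is one derived variable and one or two tables, with no new data, visits or procedures.

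One limit remains. Apart from an Early Termination visit, no ECG is scheduled between the pre-dose recording and Day 22, so QTcF will not show an effect soon after infusion. The study report should say so.

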7.13.4. Clinical Laboratory Tests

Standard clinical laboratory profiles for safety assessments (including chemistry, hematology, coagulation, and urinalysis) will be collected and evaluated at the Randomization Visit (Day 1 pre-dose).

Blood samples for chemistry, hematology, and coagulation will be obtained on Days 2 (+1 day), 4 (± 1 day), and 6 (± 1 day) of the Monitoring Period, or Early Termination (if applicable and if clinically indicated). During Week 2 (Day 8 through Day 14) and/or Week 3 (Day 15 through Day 21) of the Monitoring Period, clinical laboratory assessments of chemistry, hematology, and coagulation will be performed twice a week while the subject remains hospitalized.

Urine for urinalysis will be obtained at the Randomization Visit (Day 1 pre-dose), on Day 6 (± 1 day) of the Monitoring Period, or Early Termination (if applicable and if clinically indicated).

Below is a list of clinical laboratory analytes to be assessed:

Chemistry

Alanine aminotransferase (ALT)	Albumin
Alkaline phosphatase	Aspartate aminotransferase (AST)
Bicarbonate	Blood urea nitrogen
Calcium	Chloride
Creatinine	Direct bilirubin
Glucose	Phosphorus
Potassium	Sodium
Total bilirubin	Total protein

Hematology

Hematocrit	Hemoglobin
Platelet count	Red blood cell (RBC) count
White blood cell (WBC) count with differential (basophils, eosinophils, lymphocytes, monocytes, and neutrophils)	RBC indices: mean corpuscular volume (MCV), mean corpuscular hemoglobin (MCH), %Reticulocytes

Coagulation

Prothrombin time	Partial thromboplastin time (PTT)
------------------	-----------------------------------

Urinalysis

pH	Blood
Ketones	Specific Gravity
Leukocyte esterase	Bilirubin
Glucose	Nitrite
Protein	

Other Screening Tests as needed (for female subjects of childbearing potential only)

Urine and/or serum pregnancy test

Descriptive statistics will be provided for hematology, chemistry, urinalysis, and coagulation parameters and change from baseline by each scheduled time point.

Shift tables from baseline to the worst post-baseline value will be provided for selected chemistry parameters (Alanine aminotransferase, Aspartate aminotransferase, Total Bilirubin, Creatinine, and Alkaline phosphatase) and hematology parameters (Hematocrit, Hemoglobin, Platelets, White blood cell count and differential). Both scheduled and unscheduled visits will be considered. For chemistry parameters, the following categories will be used: <LLN, normal, >ULN and 3×ULN, >3×ULN to 5×ULN, >5×ULN, and missing. For hematology parameters, the following categories will be used: low, normal, high, and missing.

The number and percentage of subjects with the following PCS abnormal liver function test will be summarized:

- ALT 3×ULN, 5×ULN, 10×ULN, and 20×ULN
- AST 3×ULN, 5×ULN, 10×ULN, and 20×ULN
- ALT or AST 3×ULN, 5×ULN, 10×ULN, and 20×ULN

- Total bilirubin 1.5×ULN and 2×ULN
- ALP 1.5×ULN and 3×ULN
- ALT or AST 3×ULN and Total bilirubin 2×ULN
- Potential Hy's Law cases: ALT or AST 3×ULN, Total bilirubin 2×ULN, and ALP 2×ULN

A listing of subjects with any post-baseline abnormal liver function tests will be presented.

All clinical laboratory data will be listed. Values outside the normal ranges will be flagged.

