7.12. Subgroup Analyses

The following subgroups will be used for subgroup analyses for the primary efficacy endpoint in the MITT and PP Populations, i.e. whether the subject has or doesn't have of *S. aureus* pneumonia up to, but not including, Day 22 for both SDO1 and SDO2

populations. The exploratory efficacy endpoints, the incidence of all pneumonias, and the incidence of other non-*S. aureus* pneumonias up to, but not including, Day 22 in the MITT and PP Populations, will also undergo the following subgroup analyses.

- Corrected Randomization stratification (Receipt or Non-Receipt of concomitant anti-staphylococcal antibiotics at the time of randomization that are potentially active against *S. aureus* pneumonia.)
- Type of ICU (e.g., SICU, MICU, Neuro ICU, Trauma ICU)
- Type of mechanical ventilation (Tracheotomy or Non-Tracheotomy) at Randomization
- Length of stay in the intensive care unit (ICU) post-treatment (<5, 5-12, >12-22, and >22 days)
- Duration of mechanical ventilation before randomization (48 vs. >48 hours)
- Baseline MRSA/MSSA from qualifying ETA culture
- Pneumonia MRSA/MSSA
- Reason for mechanical ventilation
- BMI categories: <25, 25-<30, 30-<35, and 35
- Age: <50, 50-<65, and >65
- WBC $\times 10^9/L$ at Baseline: <1, 1 to <2.5, 2.5 to <5, 5 to <10, and >10
- Platelet count $\times 10^9/L$ at Baseline: <50, 50 to <150; 150 to <400, and > 400
- Change in platelet count from Baseline: decrease by 50% or greater, or an increase by 50% or greater
- Male vs. female
- Smoker vs. non-smoker
- History of COPD vs. non-COPD
- History of alcohol use vs. no history of alcohol use
- Hospital readmission within 30 days after discharge
- Qualifying ETA and Screening ETA cultures: *S. aureus* only vs. co-colonized *S. aureus* and any Gram-negative at any time before randomization vs. co-colonized *S. aureus* and any other organism at any time before randomization
- Procalcitonin at Baseline for those who develop pneumonia vs. those who don't develop pneumonia: <median vs. median
- Qualifying ETA culture: *S. aureus* 3+ vs. 4+ vs. Heavy
- Cardiac events yes/no from receipt of study drug to Day 90 or early termination
- Multi organ failure yes/no from receipt of study drug to Day 90 or early termination

- Acute kidney injury defined by an absolute increase in serum creatinine of 0.3 mg/dL or a 50% increase (*viz.*, 0.3 mg/dL increase if baseline = 0.6 mg/dL and 50% increase if baseline is = 0.6 mg/dL) within 48 hours from receipt of study drug

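### Hematology shift tables use one undefined 'worst' value per subject, so a subject with both a low and a high platelet, WBC or differential count is shown under only one

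*SAP*

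**What the plan says.** SAP 7.13.4 (Clinical Laboratory Tests) plans shift tables for five chemistry parameters and for hematocrit, hemoglobin, platelets, WBC and differential: "Shift tables from baseline to the worst post-baseline value will be provided". On visits it adds: "Both scheduled and unscheduled visits will be considered". On categories: "For hematology parameters, the following categories will be used: low, normal, high, and missing".

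The chemistry categories in the same paragraph are graded upward in multiples of the upper limit of normal, so 'worst' reads naturally as highest for the liver tests and creatinine. For hematology there is no grading, no definition of 'worst', no precedence between low and high, and no separate low and high tables.

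Hematology is drawn on Days 2, 4 and 6. In Weeks 2 and 3, "clinical laboratory assessments of chemistry, hematology, and coagulation will be performed twice a week while the subject remains hospitalized". There is a further draw on Day 22 (Protocol 6.5.3; SAP Table 1).

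**The concern.** For platelets, WBC and differential counts, both ends of the range are abnormal. One value per subject and parameter means one post-baseline category. With repeated draws in ventilated ICU patients, one subject may have a low value at one visit and a high value at another. Any rule that picks a single value then omits the other abnormality from the table.

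At stake is a plain safety question: how many subjects in each arm ever had a low count, and how many ever had a high one. Safety is part of the primary objective (SAP 4.1.1), laboratory parameters are a safety endpoint (SAP 5.2.7), and the protocol calls this the first study in this population (Protocol 5.3). The hematology shift is the only planned by-arm table built on each subject's extreme value, so an understatement there is not made good by another table.

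**Working it through.** The plan states no figure on this point, so there is none to reproduce. The check has four steps.

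**1. Can one subject have both?** Scheduled post-baseline draws for a subject hospitalized through Day 22: 3 (Days 2, 4, 6) + 2 (Week 2) + 2 (Week 3) + 1 (Day 22) = 8, plus any unscheduled draws. Subjects discharged earlier have fewer. Both a low and a high value are possible.

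**2. Does the wording settle the category?** Assume platelet limits of 150 and 400 (×10⁹/L). The SAP gives no reference range; these are two of the baseline platelet band edges in SAP 7.12. Take a subject with a lowest value of 90 and a highest of 650.

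- Distance beyond the limit: 150 − 90 = 60 below; 650 − 400 = 250 above. Worst is high.
- Ratio to the limit: 150/90 = 1.67; 650/400 = 1.63. Worst is low.

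Two reasonable rules put the same subject in different categories, and each omits a real abnormality. Defining 'worst' would make the table reproducible but would not recover the omitted value.

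**3. How many subjects could be affected?** The documents give no rates of low, high or both. Assume a share L ever low and a share H ever high, independent, with the 177 subjects per arm planned for randomization (SAP 6). Subjects with both = 177 × L × H.

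| L | H | Ever low | Ever high | Both | Low shown if high takes precedence | High shown if low takes precedence |
|---|---|---|---|---|---|---|
| 10% | 30% | 17.7 | 53.1 | 5.3 | 12.4 | 47.8 |
| 20% | 50% | 35.4 | 88.5 | 17.7 | 17.7 | 70.8 |
| 30% | 70% | 53.1 | 123.9 | 37.2 | 15.9 | 86.7 |

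Over this range, a rule favouring high would leave out 5.3 to 37.2 of the ever-low subjects per arm, which is a share H (30% to 70%) of them. A rule favouring low would leave out the same number of ever-high subjects, a share L (10% to 30%). Without independence the overlap is wider still. In the middle row it could lie anywhere from 0 to 177 × 20% = 35.4. The table shows only how the loss depends on the overlap; it predicts nothing about this trial.

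**4. Does another planned output give the count?**

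- Descriptive statistics and change from baseline at each scheduled time point (SAP 7.13.4) describe visits. They do not count subjects ever outside the range.
- Threshold counts by arm (SAP 7.13.4) cover liver tests only.
- Listings flag every out-of-range value (SAP 7.13.4) but make no comparison by arm.
- Adverse event tables by arm (SAP 7.13.1) include a low or high count only if the investigator judged it clinically significant (Protocol 9.1).

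None gives the number of subjects ever low or ever high by arm.

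**The case against.** The best defence is that the SAP is silent rather than wrong. It speaks of tables in the plural, so a worst-low and a worst-high shift might be intended, and SAP 8.2 leaves table format to a separate specification that is not among the documents. This does not carry far. The plural is explained by the list of parameters, while the value each table shifts to is singular. The separate specification is described as covering format, and the choice of summary value is an analysis decision.

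The second defence stands in large part: little information is truly lost. An early fall contributes to the early-visit summaries whatever happens later, every out-of-range value is listed and flagged, and a clinically significant abnormality should be reported as an adverse event and tabulated by arm. The gap therefore lies mainly in abnormalities not judged clinically significant.

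Three stronger readings are tempting, and the documents support none of them.

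- A reader might infer that low counts will be hidden by later highs. Nothing says high takes precedence. A high can equally be hidden by a low, and time order does not matter to a worst-value rule.
- A reader might infer that the loss is selective, because high counts can follow infection and ASN100 is meant to reduce infection. No rates are given from which to judge this. If infection were the driver and ASN100 worked, fewer ASN100 subjects would have a high value, so under a rule favouring high fewer ASN100 lows would be displaced. That would not conceal an excess of lows on ASN100. Other causes of a high count could act the other way, so the direction is unknown.
- A reader might take the SAP 7.12 item "Change in platelet count from Baseline: decrease by 50% or greater, or an increase by 50% or greater" as showing that the safety plan tracks both directions. It is a subgroup for efficacy endpoints; it neither supports the concern nor closes the gap.

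**Conclusion.** The point holds as a minor reporting gap. On the SAP's wording, each subject has one hematology shift per parameter to one undefined worst value. A subject with both a low and a high platelet, WBC or differential value is shown under only one, so the by-arm count of subjects ever low or ever high can be understated. Which one is lost is undefined.

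The size cannot be estimated from the documents. The figures in the working rest on assumed rates, on independence, and on the planned 177 per arm rather than the actual Safety Population. The documents do not support a claim that the loss favours either arm. Efficacy, sample size and clinical management are unaffected.

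**What to change.** In SAP 7.13.4, for platelets, WBC and each differential count, replace the single shift with two: baseline to the lowest post-baseline value, and baseline to the highest. Keep the existing categories, use scheduled and unscheduled visits, and present both by actual treatment in the Safety Population. Every subject ever low and every subject ever high is then counted. In the middle row of the illustration, all 35.4 ever-low and all 88.5 ever-high subjects would appear. Doing the same for hemoglobin and hematocrit is optional.

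The cost is a wording change and a few extra tables from data already collected. SAP Section 3 allows the plan to be modified before the data are unblinded, and the change should be made by then.

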### 1.3 Risk/Benefit

In mechanically ventilated subjects heavily colonized with *S. aureus*, ASN100 may prevent *S. aureus* pneumonia, a condition associated with significant morbidity and mortality and representing a significant unmet clinical need.

The ASN100 drug components ASN-1 and ASN-2 are fully human mAbs belonging to the IgG1 immunoglobulin subclass glycoproteins. They share a high degree of sequence homology with endogenous IgGs of the same subclass (approximately 90% to 95%) and are manufactured using standard mammalian cell expression and purification technologies (including 4 orthogonal viral clearance steps); therefore, they are expected to carry mammalian glycosylation pattern and to continue to be well tolerated in humans.

The target toxins recognized by ASN-1 and ASN-2 are bacterial, non-human, and are not expressed in human tissues. Lack of off-target reactivity is supported by the results of human tissue cross-reactivity studies involving a panel of 33 tissue types that demonstrated no cross-reactivity with human tissues. The antibody function of ASN100 is based solely on neutralization; complement-dependent cytotoxicity and antibody-dependent cell-mediated cytotoxicity (ADCC) mechanisms in the mode of action are irrelevant. ASN-1 and ASN-2 cannot bind to toxins already bound to human tissues and therefore unwanted ADCC reactions toward human cells and tissues is unlikely.

A single ascending dose study conducted with ASN100 in doses up to 8000 mg (i.e., 4000 mg ASN-1 and 4000 mg ASN-2) demonstrated that ASN100 was well tolerated with no reported related SAEs and 2 reported possibly related adverse events of headache and fatigue. No dose-limiting toxicity was observed up to the highest dose tested.

The potential immunogenicity of the antibodies and resulting immune complex formation following the production of anti-drug immunoglobulin M and IgG antibodies by the host immune system cannot be excluded; however, the risk for this outcome is considered to be low.

ASN100 belongs to the class of mAbs targeting foreign (bacterial), non-human antigens and is expected to yield a low risk of adverse events resulting from immunogenicity due to the single-dose administration used in this study.

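### Some creatinine rises that meet the SAP's own acute kidney injury definition show as no shift in the planned creatinine table, and no Section 7.13 output counts them by arm

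*SAP*

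**What the plan says.** SAP 7.13.4 includes creatinine among the shift-table parameters: "Shift tables from baseline to the worst post-baseline value will be provided for selected chemistry parameters (Alanine aminotransferase, Aspartate aminotransferase, Total Bilirubin, Creatinine", with alkaline phosphatase completing the list. One set of categories serves all five: "For chemistry parameters, the following categories will be used: <LLN, normal, >ULN and 3×ULN, >3×ULN to 5×ULN, >5×ULN, and missing". I read the third category as above ULN up to 3×ULN; a comparison sign is missing from the text I have, and I do not treat that as an error in the plan.

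The same section adds a threshold table for liver tests only: "The number and percentage of subjects with the following PCS abnormal liver function test will be summarized". Its first ALT line reads "ALT 3×ULN, 5×ULN, 10×ULN, and 20×ULN", so the 3× and 5× boundaries of the shift table are also the first two ALT cut points. Creatinine has no threshold table.

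The SAP does define kidney injury, in 7.12: "Acute kidney injury defined by an absolute increase in serum creatinine of 0.3 mg/dL or a 50% increase", counted within 48 hours of study drug. The definition sits in a list introduced by "The following subgroups will be used for subgroup analyses for the primary efficacy endpoint in the MITT and PP Populations". That list also serves two pneumonia incidence endpoints. SAP 7.11 analyses efficacy by randomized group; SAP 7.13 analyses safety by treatment received.

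Creatinine otherwise appears in Section 7.13 only as descriptive change from baseline by visit and in listings flagged against the normal range.

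**The concern.** The SAP measures kidney injury in 7.12 as a change from the subject's own baseline. The safety shift table in 7.13.4 measures creatinine by its position against a reference range, in bands wide enough for liver enzymes. The two scales can disagree about the same subject, and only the second is planned as a safety output.

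Safety and tolerability are part of the primary objective (Protocol 2.1), and Protocol 5.3 calls this the first study in this population. Background kidney injury is to be expected in ventilated intensive care patients, so a by-arm count on an objective rule tells more than attribution case by case. The plan already derives such a rule but does not tabulate it in the safety section.

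**Working it through.** **Inputs**

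- AKI rule: 0.3 mg/dL or 50%, within 48 hours (SAP 7.12).
- Shift boundaries: LLN, ULN, 3×ULN, 5×ULN (SAP 7.13.4), with the worst post-baseline value taken from scheduled and unscheduled visits.
- Creatinine reference range: not given in the documents. I assume ULN 1.2 mg/dL (range 1.0 to 1.4) and LLN 0.5 mg/dL.

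**Step 1: reproduce the SAP's own figure.** The rule switches criterion at a stated baseline: "0.3 mg/dL increase if baseline = 0.6 mg/dL and 50% increase if baseline is = 0.6 mg/dL". The two criteria coincide where 0.50 × baseline = 0.3, so baseline = 0.3 / 0.50 = 0.6 mg/dL, which matches. The directions of the two comparisons are missing from the text I have, so I ran both readings: the smaller and the larger of 0.3 mg/dL and 50%.

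**Step 2: width of the category, for any ULN.** 3×ULN / ULN = 3. A subject who starts just above ULN can rise by just under threefold and stay in the same cell.

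**Step 3: baselines from which a just-qualifying AKI shows no shift.** Starting in the normal range, the highest such baseline is ULN − 0.3 (0.3 mg/dL criterion) or ULN / 1.5 (50% criterion). Starting above ULN, it is 3×ULN − 0.3 or 3×ULN / 1.5.

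| Assumed ULN (mg/dL) | Normal, 0.3 criterion | Normal, 50% criterion | Above ULN, 0.3 criterion | Above ULN, 50% criterion |
|---|---|---|---|---|
| 1.0 | 0.7 | 0.67 | 2.7 | 2.0 |
| 1.2 | 0.9 | 0.8 | 3.3 | 2.4 |
| 1.4 | 1.1 | 0.93 | 3.9 | 2.8 |

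**Step 4: examples at ULN 1.2 mg/dL (3×ULN = 3.6).**

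- 0.6 to 1.1: rise 0.5 mg/dL, 1.1 / 0.6 − 1 = 83%. AKI on either reading; normal to normal.
- 1.4 to 3.4: rise 2.0 mg/dL, 3.4 / 1.4 − 1 = 143%. AKI on either reading; same cell.
- 1.0 to 1.5: rise 0.5 mg/dL, 50%. AKI, and it does cross ULN, so this one is seen.

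The SAP's baseline renal disease cut of 2 mg/dL (7.12) is 2 / 1.2 = 1.67×ULN, inside the same wide cell.

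**Step 5: share of AKI cases shown as no shift.** This needs distributions that the documents do not give, so all inputs here are assumed.

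| Assumed model | Smaller threshold | Larger threshold |
|---|---|---|
| A. Log-normal baseline, median 0.7 to 1.1 mg/dL, log-SD 0.3 to 0.5; median rise 1.2 to 2 times the threshold; ULN 1.0 to 1.4 | 20% to 76% | 15% to 62% |
| B. Log-normal baseline, median 0.8 to 1.1 mg/dL, log-SD 0.45; peak/baseline half-normal on the log scale, SD 0.45; ULN 1.1 to 1.3 | 39% to 51% | 31% to 38% |
| C. As B, with a further rise after 48 hours (half-normal, log-SD 0.2 to 0.45) | 18% to 39% | 12% to 26% |

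Model C matters because AKI is judged within 48 hours while the shift table takes the worst value at any time, so a later rise can move a case into a higher cell. Models B and C also imply AKI in a third to more than half of all subjects, which no document supports; only the share among AKI cases is used here. Overall the range is about 12% to 76%.

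**The case against.** The strongest reply is that kidney injury has other routes into the report, and this is right as far as it goes.

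- **Adverse events.** A reader might infer that the safety tables as a whole would miss kidney injury. They would not. Protocol 9.1 requires all adverse events to be recorded, and prefers a named disease to its signs. The clinical significance judgement applies to isolated laboratory findings. A diagnosed kidney injury therefore reaches the tables of treatment-emergent events, but a creatinine rise that nobody diagnoses or judges significant need not.
- **Subgroup denominators.** A reader might also infer that AKI is never shown by arm. The 7.12 subgroup tables should carry the number with AKI in each arm, and the MITT Population should be close to the Safety Population. That count would still be by randomized group, in MITT and PP, and presented as an efficacy split.
- **Listings and visit summaries.** These exist, but the listing flag misses a rise within the normal range, and visit summaries count no subjects.
- **Immune complexes.** It is tempting to argue that renal harm is expected because Protocol 1.3 says of "The potential immunogenicity of the antibodies and resulting immune complex formation" that it cannot be excluded. The same sentence calls the risk low and does not mention the kidney. It also describes a process that follows a host antibody response, which fits a 48-hour window poorly. The point does not rest on this.
- **Size.** A narrow figure such as 39% to 51% depends on one reading of the rule and on one peak serving both scales. The documents do not support that precision, nor a claim that most cases would be lost.

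**Conclusion.** The point holds as a partial gap in safety reporting. Two things follow from the text alone: the creatinine shift table can show no shift for a rise of just under threefold, and no Section 7.13 output counts subjects by rise from baseline. The mg/dL examples need an assumed ULN. The share of AKI cases affected cannot be fixed from the documents; 12% to 76% describes the assumptions, not the trial. The documents do not support a claim that kidney injury would go unreported, or that a difference between arms would be diluted by a known amount. The plan does not contradict itself here, and the primary analysis, alpha and sample size are untouched. The change is worth making because it is cheap and serves the safety part of the primary objective.

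**What to change.** Keep the creatinine shift table; it still displays worst values. Add to SAP 7.13.4 one table with the count and percentage of subjects who meet the 7.12 AKI definition, by actual treatment in the Safety Population, with the difference between arms and its 95% CI.

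A summary of the maximum post-baseline to baseline creatinine ratio through Day 22 may be added. It should be labelled as a new summary, because the 7.12 definition stops at 48 hours.

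The cost is a short SAP edit and one or two tables from chemistry values already scheduled (Day 1 pre-dose, Days 2, 4 and 6, twice weekly in Weeks 2 and 3 while hospitalized, and Day 22). SAP section 3 allows changes before unblinding. The downside is one more table in which background intensive care kidney injury will appear in both arms, so it should be read as a comparison and not as a rate caused by treatment.
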